6.2.3 Handling of Missing Data

In general, values for missing data will not be imputed, unless methods for handling missing data are specified.

For MMRM analysis, no imputation will be performed for missing viral shredding. If a patient misses a visit, the missing data will not be imputed. The mixed effect model will handle missing data based on a likelihood method under the "missing at random" assumption.

Sensitivity analyses using method of last observation carry forward (LOCF) may be considered to assess the potential impact from missing data for MMRM in primary analysis.

Missing dates or partially missing dates will be imputed conservatively for adverse events and prior/concomitant medications/procedures. Specific rules for handling of missing or partially missing dates for adverse events and prior/concomitant medications/procedures are provided in Appendix 10.1.

By-visit endpoints will be analyzed using observed data, unless otherwise specified. For observed data analyses, missing data will not be imputed and only the observed records will be included.

Censoring rules for analyses of time-to-event endpoints are determined as in [Table 1](#).

Table 1 Censoring Rules for Analyses of Time-to-event Endpoints

No.	Situation	Date of Event or Censoring	Outcome
1	Target event documented	Date of occurrence of target event	Event
2	Multiple target events documented	Date of first occurrence of target event	Event
3	No target event or death occurred by the time of the End-of-Study Visit or data cut-off, whichever comes first	Date of the End-of-Study Visit or data cut-off, whichever comes first	Censored
4	Death and no target event prior to death	Date of data cutoff	Censored

6.2.4 Multiplicity Adjustment

The MCPMod procedure allows for simultaneous evaluation of different potential dose response patterns, whilst protecting the overall probability of Type I error (one-sided α of 5%). No additional multiplicity adjustments will be made in this study. Two-sided 90% confidence interval will be used to describe the precision of the rate estimate whenever appropriate.

6.2.5 Data Integrity

Before pre-specified interim or final statistical analysis begins, the integrity of the data should be reviewed to assure fit-for-purpose. The data set for analysis should be an accurate and complete representation of the subjects' relevant outcomes from the clinical database. All data should be completed and reviewed up to a pre-specified cutoff date. Consistency checks and appropriate source data verification should be completed.

6.3 SUBJECT CHARACTERISTICS

6.3.1 Patient Disposition

The number of patients randomized, treated, discontinued from study drug and/or the study will be counted. The primary reason for study drug and/or study discontinuation will be summarized according to the categories in the eCRF.

6.3.2 Protocol Deviations

Important protocol deviation criteria will be established and patients with important protocol deviations will be identified and documented before the database lock.

Important protocol deviations will be summarized for all patients in the Safety Analysis Set and

listed by each category.

6.3.3 Demographic and Other Baseline Characteristics

Demographic and other baseline characteristics will be summarized using the ITT Analysis Set and descriptive statistics. Continuous variables include but are not limited to age, weight for determining drug administration, and time from first COVID-19 symptom to date of drug administration. Categorical variables include but are not limited to age group, gender, country, race, disease severity, serology status, baseline viral load level group in nasopharyngeal swab samples, and risk status.

High risk is defined as patients who meet at least one of the following criteria:

- Have a body mass index (BMI) ≥ 35
- Have chronic kidney disease
- Have diabetes
- Have immunosuppressive disease
- Are currently receiving immunosuppressive treatment
- Are ≥ 65 years of age
- Are ≥ 55 years of age AND have
 - cardiovascular disease, OR
 - hypertension, OR
 - chronic obstructive pulmonary disease/other chronic respiratory disease

6.3.4 Prior and Concomitant Medications

Prior medications will be defined as medications that stopped before the administration of study drug. Concomitant medications will be defined as medications that 1) started before the administration of study drug and were continuing at the time of the administration of study drug, or 2) started on or after the date of the administration of study drug up to 30 days after dosing.

Concomitant medications will be coded using the World Health Organization Drug Dictionary drug codes and will be further coded to the appropriate Anatomical Therapeutic Chemical code indicating therapeutic classification. Prior and concomitant medications will be summarized and listed by drug and drug class. A listing of prior and concomitant medications will be provided.

6.3.5 Medical History

Medical History will be coded using MedDRA (version 23.0 or newer). The number (percentage) of subjects reporting a history of any medical condition, as recorded on the eCRF, will be summarized by system organ class and preferred term in the safety analysis set. A listing of medical history will be provided.

6.4 EFFICACY ANALYSIS

6.4.1 Primary Endpoint Analyses

The statistical hypotheses to be tested for the primary endpoint are as follows:

H_0 : there is a flat dose response curve comparing change from baseline to Day 8 in SARS-CoV-2 viral shedding in the placebo and the BGB-DXP593 dose groups

H_1 : there is a non-flat dose response curve indicating a benefit of BGB-DXP593 over placebo

[figure not shown]
A Mixed Model Repeated Measures (MMRM) analysis will be used to analyze the primary endpoint of change from baseline to Day 8 in SARS-CoV-2 viral shedding. This model will include treatment, visit, and disease severity at baseline as discrete fixed effects; baseline viral shedding as a continuous fixed effect; and interaction between visit and treatment, interaction between visit and baseline, and patient as a random effect. The primary treatment comparisons will be the contrast between treatments at Day 8.

The analysis will be carried out and covariate-adjusted fixed effect estimates of average response for each treatment and the covariance matrix will be extracted from the fit and used for multiple comparison procedures and modelling approaches (MCPMod) analysis.

The primary analysis uses methodology for dose finding employing both multiple comparison procedures and modelling techniques. The MCPMod procedure allows for simultaneous evaluation of different potential dose response patterns, whilst protecting the overall probability of Type I error (one-sided α of 5%).

For the hypothesis testing and for the sample size calculation, the basic shape of each of the models to be tested must be predefined. The following models will be considered for this analysis: linear, Emax, SigEmax and quadratic.

The model assumptions and resulting graphs were selected to cover both plausible and a diverse range of dose response patterns. These are shown in [Figure 2](#). The parameters for each model shape are listed in [Table 2](#).

Figure 2: Shape of the Considered Dose Response Patterns for the MCPMod Analysis

Abbreviation: MCPMod, multiple comparison procedures and modelling approaches

Table 2: Parameter(s) in Each Model

Model	Prespecified parameters
Emax1	ED ₅₀ =2.6
Emax2	ED ₅₀ =12.5
sigEmax	ED ₅₀ = 10, h=4
Quadratic	$\delta = -0.022$
Linear	No assumption needed

If at least one model is statistically significant, then we will reject the null hypothesis of a flat dose response relationship over viral shedding change at Day 8, with a multiple contrast test controlled for the family-wise type I error rate at one-sided $\alpha = 5\%$. A one-sided p-value that corresponds to the most significant model will be calculated.

Bootstrap method with treatment effect resamples is used to induce dose-response relationship. Four candidate models (E_{max}, sigE_{max}, Quadratic, and Linear) are fitted and the one with lowest gAIC is selected separately for each resample. The target dose(s) can be estimated from the average model using bootstrap method by incorporating information on the target treatment effect and by accounting for safety. Denote by U_d the upper 0.95 percentile of confidence limit of the predicted mean value p_d at dose d based on the dose-response relationship, where $d = d_1$ (placebo), d_2 (5mg/kg), d_3 (15mg/kg), and d_4 (30mg/kg). The target dose can be found by

$$TD = \operatorname{argmin}_{d \in \{d_1, d_k\}} \{p_d < p_{d_1} + \Delta, U_d < p_{d_1}\}$$

where $k = 1, 2, 3$, and 4. The target treatment effect, Δ , is set to $-1 \log_{10}$ copies/ml.

Comparisons of active doses to placebo (90% confidence intervals [CIs] and p-values) based on the mixed effects model will be reported. These are supportive analyses of the primary endpoint to supplement the MCPMod analysis, which is the primary analysis.

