6. PRIOR AND CONCOMITANT THERAPY

6.1. Permitted Concomitant Medications/Procedures

Unless noted otherwise, most concomitant medications and therapies deemed necessary and in keeping with local standards of medical care at the discretion of the investigator for a patient's welfare are allowed. Standard of care therapy for mild to moderate COVID-19 is allowed according to local treatment guidelines.

All concomitant medications, including all prescription and over-the-counter drugs, supplements, and intravenous medications and fluids, taken by or administered to the patient within 30 days before the study drug administration and during the study will be recorded in the eCRF including indication and dates of administration.

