10.1.2. Randomization Methods

Patients will be randomized using the IRT system with allocation ratio of 1:1:1:1 to placebo, BGB-DXP593 at 5 mg/kg, BGB-DXP593 at 15 mg/kg, and BGB-DXP593 at 30 mg/kg. Patient randomization will be stratified by country and disease severity (mild versus moderate COVID-19).

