4.3 EXPLORATORY ENDPOINTS

5 SAMPLE SIZE CONSIDERATIONS

The sample size calculation is based on the following assumptions:

- The primary endpoint “change from baseline to Day 8 in SARS-CoV-2 viral shedding” is normally distributed
- One-sided significance level $\alpha = 5\%$
- True maximum treatment effect size of BGB-DXP593 versus placebo is $-1.5 \log_{10}$ copies per mL
- Standard deviation is $3.2 \log_{10}$ copies per mL (Wang et al 2020)
- Prespecified candidate models listed in Section 6.4.1

Forty-one patients are needed with primary endpoint data per arm to provide at least 82% power to detect non-flat dose-response relationship. MCPMod approach is used. In order to ensure 41 patients per arm with primary endpoint data, at least 43 patients per arm need to be randomized to account for potential dropout rate of 5%.

The calculation has been performed using R software, version 3.6.1.

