6.4.2 Secondary Endpoint Analyses

Secondary efficacy endpoints will include:

- Time-weighted average change in viral shedding as measured by RT-qPCR in nasopharyngeal swab samples from baseline to Day 15
- Change in SARS-CoV-2 viral shedding as measured by RT-qPCR in nasopharyngeal swab samples from baseline to Day 15
- Time to negative RT-qPCR in all tested samples with no subsequent positive RT-qPCR in any tested samples
- Proportion of patients requiring hospitalization due to worsened COVID-19
- Time to resolution of all COVID-19-related symptoms
- All-cause mortality rate at Day 29

The time-weighted average change in viral shedding as measured by RT-qPCR in nasopharyngeal swab samples from baseline to Day 15 is defined as:

$$\frac{\sum_{i=a}^{b-1} [0.5 \times (Y_i + Y_{i+1}) \times (t_{i+1} - t_i)]}{t_b - t_a}$$

where Y_i is the change from baseline in viral shedding at Visit i , t is the time at the specified timepoint (the actual study day), a is the baseline assessment at Day 1, and b is the last assessment at or prior to Day 15 visit. Analysis of covariance (ANCOVA) model with corresponding baseline viral shedding, disease severity at baseline, and treatment as covariates will be used. Comparisons of active doses to placebo (90% CIs and p-values) will be provided.

The same MMRM analysis for primary endpoint will be used to analyze the change in SARS-CoV-2 viral shedding from baseline to Day 3 and Day 15. Comparisons of active doses to placebo (90% CIs and p-values) will be provided.

[figure not shown]
The negative RT-qPCR is defined as the value that is below the lower limit of detection. Kaplan-Meier method will be used to assess the time to negative RT-qPCR. The corresponding quartiles (including the median) will be reported and a two-sided 90% CI of median, if estimable, will be constructed with a generalized Brookmeyer and Crowley method for each dosing group. Patients who have died prior to experiencing the event of interest will be censored on the day of data cutoff. Patients for whom the RT-qPCR value is still positive by the time of end of study visit or data cutoff, whichever comes first, will be censored on the last RT-qPCR sample date.

[figure not shown]
The number of patients who require hospitalization due to worsened COVID-19 will be counted. Corresponding proportion will be derived and a two-sided binomial exact 90% CI of proportion will be constructed.

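### The viral-load models omit country, a randomisation stratum, and the primary MMRM leaves its within-patient covariance unspecified

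*SAP*

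**What the plan says.** Protocol 10.1.2 gives the strata: "Patient randomization will be stratified by country and disease severity (mild versus moderate COVID-19"; SAP Section 2 repeats them.

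SAP 6.4.1 defines the primary MMRM: "This model will include treatment, visit, and disease severity at baseline as discrete fixed effects; baseline viral shedding as a continuous fixed effect", then visit-by-treatment, "interaction between visit and baseline, and patient as a random effect". Protocol 10.2.1 has the same model plus a visit-by-severity interaction. Neither document's model contains country. In the readable SAP, country otherwise appears only as a stratification factor and a baseline characteristic (6.3.3). Neither document names a residual covariance structure, a fallback if the fit does not converge, or a degrees-of-freedom method.

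The fit supplies the primary test. The adjusted treatment means and "the covariance matrix will be extracted from the fit and used for multiple comparison procedures and modelling approaches (MCPMod) analysis". In SAP 6.4.2 the same model "will be used to analyze the change in SARS-CoV-2 viral shedding from baseline to Day 3 and Day 15", and the time-weighted average has its own model: "Analysis of covariance (ANCOVA) model with corresponding baseline viral shedding, disease severity at baseline, and treatment as covariates will be used". The Protocol's Appendix 1 schedules post-baseline nasopharyngeal swabs on Days 3, 8 and 15.

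**The concern.** There are two separate gaps.

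**Country.** Stratification balances country across arms, so country adds nothing to the true sampling variance of the treatment difference. A model without country still counts its variance as residual noise. If country is prognostic, the reported standard error is too large, the test is conservative and power is lost. A country effect is possible because background care varies: "Standard of care therapy for mild to moderate COVID-19 is allowed according to local treatment guidelines".

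**Within-patient covariance.** A single random intercept with independent residuals is compound symmetry, meaning one variance for all visits and one correlation for all pairs of visits. The Day 8 standard error then borrows its variance from Days 3 and 15. MCPMod takes its covariance matrix from this fit, so the one-sided 5% family-wise claim depends on the borrowed variance. So do the Day 3 and Day 15 comparisons.

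**Working it through.** **Inputs from the documents.** Doses 0, 5, 15 and 30 mg/kg; the five shapes in SAP Table 2; one-sided 5%; 41 evaluable per arm; maximum effect 1.5 log10 copies/mL; SD 3.2 (SAP Section 5). Visit-specific SDs, the variance explained by country, the number of countries and the accrual time are not given. Values used for them below are assumptions.

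**The plan's own figure.** The SAP states: "Forty-one patients are needed with primary endpoint data per arm to provide at least 82% power to detect non-flat dose-response relationship". Optimal contrasts for the five shapes, with 160 degrees of freedom, give a simulated critical value of 1.94. Power is 82.2% for sigEmax and 69.8% to 72.0% for the other four shapes (77.8% for the quadratic if the 1.5 is reached at a tested dose). So 82% is reproduced for sigEmax only. That is a separate matter: the calculation uses one SD and no country term, so the present point does not alter it.

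**Country.** Without country, reported SE / true SE = 1/√(1 − R²), where R² is country's share of the residual variance after baseline load and severity. Family-wise error is P(max contrast > 1.94 × ratio).

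| R² | ratio | error, formula | error, simulated without country | error, simulated with country × visit | linear-shape power, without → with |
|---|---|---|---|---|---|
| 2% | 1.010 | 4.8% | 4.9% | 5.1% | 70.0 → 70.8% |
| 5% | 1.026 | 4.5% | 4.7% | 5.1% | 69.9 → 71.6% |
| 10% | 1.054 | 4.0% | 4.2% | 5.1% | 70.2 → 73.9% |

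The simulation used 164 patients, four countries, permuted blocks of four within country and severity, an unstructured covariance and 16,000 runs per case. Monte Carlo error is about 0.2 points on error and 0.4 on power, so the smallest gains are at the limit of resolution. For sigEmax the gains are 0.5, 1.4 and 2.7 points, from about 82–83%. With R² = 0, power goes from 70.2 to 70.0% (four countries) and from 69.6 to 69.4% (eight).

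If the country effect differs by visit (relative size 0, 1 and 0.5 at Days 3, 8 and 15), linear-shape power with no country term, a main effect only, and the visit interaction is 69.9, 71.0 and 71.6% at R² 5%. At R² 10% it is 69.8, 72.0 and 73.4%. The interaction is therefore worth including.

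**Covariance, literal random intercept, complete data.** Reported SE / true Day 8 SE = √(mean of the three visit variances) / Day 8 SD. For SDs of 2.6/3.2/4.2 at Days 3/8/15, the mean variance is (6.76 + 10.24 + 17.64)/3 = 11.55 and the ratio is 3.398/3.2 = 1.062.

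| assumed SD, Days 3/8/15 | ratio | Day 8 family-wise error |
|---|---|---|
| 2.0/3.2/3.2 | 0.893 | 7.6% |
| 2.6/3.2/3.2 | 0.942 | 6.3% |
| 2.9/3.2/3.2 | 0.970 | 5.6% |
| 3.2/3.2/3.2 | 1.000 | 5.0% |
| 2.6/3.2/3.7 | 1.00 | 5.0% |
| 2.6/3.2/3.8 | 1.012 | 4.8% |
| 2.6/3.2/4.2 | 1.062 | 3.9% |
| 3.2/3.2/4.2 | 1.114 | 3.1% |

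The 2.6/3.2/3.7 row shows what matters. Its visit variances differ widely, yet their mean, (6.76 + 10.24 + 13.69)/3 = 10.23, matches the Day 8 variance of 10.24, so the error is 5.0%. Direct simulation of the pooled-variance fit (40,000 runs, correlation 0.5) for five of these sets gives 7.5, 6.4, 5.5, 3.7 and 2.9%, against 7.6, 6.3, 5.6, 3.9 and 3.1% above. An unstructured covariance on the same data gives 4.8 to 5.1%.

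**Other visits.** With 2.6/3.2/4.2 the pooled SD is 3.398. A one-sided 5% pairwise test on Day 15 uses 1.645 × 3.398/4.2 = 1.33, an actual error of about 9.2%. On Day 3 it uses 1.645 × 3.398/2.6 = 2.15, about 1.6%.

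**Partial Day 15 data.** The primary analysis is cut once all patients have passed Day 8 or left the study. With uniform accrual over 4, 8 or 12 weeks, 1 − 1/weeks = 75, 88 or 92% of patients have Day 15 data. Day 8 error for 2.6/3.2/4.2 is then about 4.4, 4.1 or 4.0%.

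**Visit-by-severity term.** If the Day 8 severity effect lies d = 0.5 to 1.0 log10 from the fitted common effect, and 30 to 50% of patients are in one stratum (p), the SE ratio is √(1 + d²p(1 − p)/3.2²). That is an SE 0.3 to 1.2% too large, with error of 4.9 to 4.8%.

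**The case against.** **On covariance.** Both documents call the model an MMRM, a label often taken to mean an unstructured covariance, and a random patient effect does not exclude visit-specific residual variances. This stands: the defect is under-specification. But two programmers could follow the same sentence and pass different standard errors to the primary test. A reader might infer that the 5% claim is broken, or that any difference between visit variances biases the Day 8 test. The documents support neither. They do not say the model will be coded as a random intercept, they give no visit-specific SDs, and only a gap between the average visit variance and the Day 8 variance matters.

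**On country.** Protocol 8.3.1 has swabs tested in a central laboratory. Protocol 6.2 bars drugs with activity against SARS-CoV-2 within 30 days of dosing, with an exception for worsened patients. Both narrow the route by which local care could shift viral load, so a large R² should not be presumed. A reader might infer that leaving out a stratum inflates false positives, or that Protocol and SAP conflict over it. Neither is so: the omission is conservative, and the two documents agree.

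**On blacked-out text.** SAP 6.4.3, 6.4.4 and 6.8 show no text and may hold a country analysis. That would not change the primary model, which is fully visible.

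**On the visit-by-severity term.** It is in Protocol 10.2.1 but not in SAP 6.4.1, while SAP Section 8 lists no changes. A reader might infer a silent change to the primary analysis. The SAP cites protocol amendment 2.0 and the version of the protocol supplied is not visible, so a version difference cannot be excluded. The effect is negligible either way.

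**Conclusion.** The point holds as a low-cost improvement to the SAP.

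- **Country:** a modest power gain, roughly 1 to 4 points if country explains 2 to 10% of the residual variance, against about 0.2 points lost if it explains none. The R² values and the number of countries are assumptions. The 5% error rate is not threatened.
- **Covariance:** a safeguard of unknown size and direction. The 3.1% to 7.6% range shows sensitivity to assumed SDs under one reading of the text; it does not estimate the error in this trial.
- **Visit-by-severity:** a documentation note only.

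**What to change.** In SAP 6.4.1:
- add country and its visit interaction to the MMRM, pooling small countries by a rule fixed in advance and applied blind;
- replace the random patient effect with an unstructured within-patient covariance over Days 3, 8 and 15;
- name the fallback order if it does not converge (for example heterogeneous Toeplitz, then heterogeneous compound symmetry) and specify Kenward-Roger degrees of freedom;
- confirm that all Day 3, 8 and 15 data available at the Day 8 cut enter the fit.

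In SAP 6.4.2, add country to the ANCOVA with the same pooling rule.

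As a documentation step, check the visit-by-severity term against the current protocol version, then restore it or list its removal in SAP Section 8.

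The cost is SAP wording before database lock, with no new data. The price is a few degrees of freedom for country and four more covariance parameters (six instead of two), with about 172 patients.

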1.3. Study Rationale

COVID-19 is an acute respiratory syndrome caused by SARS-CoV-2 infection. BGB-DXP593 is a neutralizing mAb against the SARS-CoV-2 selected from convalescent COVID-19 patients. By binding to the RBD on the S protein of the virus, BGB-DXP593 can prevent the virus from entering the cells. Its pre- and post-exposure prophylaxis effects in hACE mice have been demonstrated (Cao et al 2020).

A few studies suggested that high viral load is associated with increased mortality (Fajnzyblber et al 2020; Pujadas et al 2020; Wolfel et al 2020). Amongst the participants hospitalized with COVID-19, higher prevalence of detectable SARS-CoV-2 plasma viral load was associated with worse respiratory disease severity, lower absolute lymphocyte counts, and increased markers of inflammation, including C-reactive protein and interleukin-6 (Fajnzyblber et al 2020). This study will explore if BGB-DXP593 can effectively reduce viral load in collected samples.

Patients who have experienced COVID-19 symptoms less than 7 days will be enrolled. By 7 days after onset of symptoms, anti-SARS-CoV-2 immunoglobulin M (IgM) or IgG can be detected in around 50% of patients (Wolfel et al 2020). Presence of anti-SARS-CoV-2 IgG in patients' blood is associated with reduced viral load. High viral loads were rare in individuals who had seroconverted (Bryan et al 2020).

This study will assess efficacy of BGB-DXP593 in lowering viral load at different dose levels. To date, there is no drug approved or recommended for mild to moderate COVID-19 (NIH COVID-19 treatment guidelines, 2020). Hence, using placebo as the control is appropriate.

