1.3.3. Rationale for Biomarker Strategy

Biomarker analyses will be performed to evaluate study treatment effects induced in patients as well as to explore potential predictive biomarkers of response to BGB-DXP593.

Seroconversion for patients with COVID-19 usually happens within the first week after symptom onset (Wolfel et al 2020). It has been shown that seroconversion occurred after 7 days in 50% of patients and almost all COVID-19 patients had neutralizing antibodies within 1 month after symptom onset, thus the existing anti-SARS-CoV-2 antibodies in patients may have an impact on the efficacy of BGB-DXP593, which is also a neutralizing antibody for SARS-CoV-2. Therefore, the baseline SARS-CoV-2 serology antibody levels may be related to the treatment effects of BGB-DXP593. Recent studies have suggested that certain mutations on SARS-CoV-2 virus may impact the infectivity and severity of the virus, especially the mutations on the receptor binding domain of SARS-CoV-2, which may also impact the neutralizing activities of SARS-CoV-2 neutralizing antibodies (Baum et al 2020; Korber et al 2020; Li et al 2020). Thus, certain mutations on SARS-CoV-2 genome may also be related to the treatment effects of BGB-DXP593.

In addition, patients with COVID-19 have shown a strong upregulation of cytokine and interferon production, it is believed that dysregulated host immune response and production of inflammatory cytokines, known as the “cytokine storm”, correlates with disease severity and poor prognosis of SARS-CoV-2 infection (Tay et al 2020). Therefore, serum cytokine levels could be a marker for evaluating disease severity and the treatment effects of anti-SARS-CoV-2 neutralizing antibodies.

Considering the immune response induced by SARS-CoV-2 infection varies a lot among different patients, all patients may not be equally likely to benefit from treatment with anti-SARS-CoV-2 neutralizing antibodies. Predictive biomarker samples collected before dosing will be assessed in an effort to identify those patients with certain gene signatures who are most likely to respond to BGB-DXP593. Thus, gene signatures at baseline and after treatment in peripheral blood may serve as predictive biomarkers and may also help to explore the mechanism of response.

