6.8 OTHER EXPLORATORY ANALYSES

7 INTERIM ANALYSIS

A primary analysis of efficacy and safety is planned after all patients have finished Day 8 visit or discontinued the study earlier. Pharmacokinetic, immunogenicity and exploratory biomarkers will not be a part of the primary analysis.

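### The primary Day 8 model leaves out baseline serostatus and symptom duration, both collected before dosing; the test stays valid, but some precision is given up and chance imbalance goes unadjusted.

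*SAP*

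**What the plan says.** The model is in SAP 6.4.1 and Protocol 10.2.1. The SAP text reads: "This model will include treatment, visit, and disease severity at baseline as discrete fixed effects; baseline viral shedding as a continuous fixed effect". It then adds visit-by-treatment and visit-by-baseline interactions and a patient effect; the protocol also has visit by severity. Neither document includes serostatus or symptom duration. Randomization is stratified by country and severity only (Protocol 10.1.2).

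The protocol explains why these two factors could matter:

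- Patients may enter up to 7 days after symptom onset (Protocol 4.1).
- Protocol 1.3 says "By 7 days after onset of symptoms, anti-SARS-CoV-2 immunoglobulin M (IgM) or IgG can be detected in around 50% of patients", and that high viral loads are rare after seroconversion.
- Protocol 1.3.3 says "Therefore, the baseline SARS-CoV-2 serology antibody levels may be related to the treatment effects of BGB-DXP593".
- Only a history of a positive serology test excludes a patient (Protocol 4.2). Serology is drawn predose on Day 1 (Protocol 8.5), and no result is required for entry.

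SAP 6.3.3 lists serology status and "time from first COVID-19 symptom to date of drug administration" as baseline characteristics to be summarized. SAP 7, on the analysis after all patients reach Day 8, says "Pharmacokinetic, immunogenicity and exploratory biomarkers will not be a part of the primary analysis". Under Protocol 10.8, that analysis informs whether to start Phase 3 and at which dose.

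**The concern.** Serostatus and time since onset both mark how far a patient's own clearance has progressed when the drug is given. The outcome is change in viral load one week later, so both are plausible predictors of it. A predictor left out of the model stays in the residual error. With 43 randomized per arm and no stratification on either factor, the arms can also differ on them by chance, and that difference passes into the adjusted Day 8 means. Those means go to the MCPMod contrasts and then to a target-dose rule that compares three doses with placebo against a threshold of -1 log10.

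A second question is whether serology will be available at the Day 8 lock. Protocol 8.5 groups it with biomarkers explored for association with efficacy, while SAP 6.3.3 treats it as a baseline characteristic. SAP 7 excludes exploratory biomarkers without saying which description applies. Because the study is unblinded after that lock (Protocol 5.5), covariates added later would be post hoc.

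**Working it through.** **Inputs from the documents.** 41 evaluable patients per arm, maximum effect -1.5 log10, SD 3.2 log10, one-sided 5% (SAP 5); doses 0, 5, 15 and 30 mg/kg with five candidate shapes (SAP 6.4.1); target effect -1 log10 (SAP 6.4.1).

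**Assumptions not in the documents.** Seropositive share at dosing s = 20-50%; the only documented figure is about 50% by day 7. Serostatus shifts the Day 8 change by d = 0.5-2 log10 beyond baseline load and severity. The residual SD of the current model is 3.2. Symptom duration is not given a separate figure.

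**1. The plan's own power.** SAP 5 states: "Forty-one patients are needed with primary endpoint data per arm to provide at least 82% power to detect non-flat dose-response relationship". An optimal-contrast MCPMod simulation (160 df, critical value 1.94) gives:

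| Shape | Power |
|---|---|
| Emax, ED50 2.6 | 72% |
| Emax, ED50 12.5 | 72% |
| sigEmax | 82% |
| Quadratic | 70% |
| Linear | 70% |

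The stated figure is reached only for sigEmax; the mean is 73%. That is a separate matter. These values serve here as the base for comparison.

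**2. Residual variance explained by serostatus**, s(1-s)d²/3.2²:

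- s = 20%, d = 0.5: 0.16 × 0.25 / 10.24 = 0.4%
- s = 50%, d = 1: 0.25 × 1 / 10.24 = 2.4%
- s = 35%, d = 1.5: 0.2275 × 2.25 / 10.24 = 5.0%
- s = 35%, d = 2: 0.2275 × 4 / 10.24 = 8.9%
- s = 50%, d = 2: 0.25 × 4 / 10.24 = 9.8%

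**3. Power after adjustment**, with SD = 3.2 × √(1 - R²):

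| R² | Linear shape | Emax, ED50 2.6 |
|---|---|---|
| 0 | 70% | 72% |
| 0.4% | +0.2 points | +0.2 points |
| 2.4% | +0.9 | +1.0 |
| 5% | +2.0 | +2.0 |
| 9% | +3.6 | +3.6 |

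The most favourable corner (9.8%) gives just under 4 points.

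**4. Chance imbalance.** The SD of the difference in seropositive share between two arms of 41 is √(2s(1-s)/41). At s = 35% this is √(2 × 0.2275 / 41) = 0.105. Multiplied by d = 1.5 or 2, it gives 0.16 or 0.21 log10. For scale, the standard error of one dose-placebo contrast is 3.2 × √(2/41) = 0.71 log10, which already contains this component. Against the -1 log10 threshold, one SD of imbalance is 16-21%.

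**The case against.** **The test is valid without these terms.** This stands. Randomization protects the type I error, and the simulated rate under a flat curve is 5.0%. A reader might infer bias or an inflated error rate; neither follows from leaving out a baseline covariate.

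**Baseline viral shedding already carries part of the signal.** This also stands. The protocol's own remark that high loads are rare after seroconversion implies it. A further shift of 1.5-2 log10 would be at least as large as the whole planned drug effect and has no source in the documents. With a 0.5-1 log10 shift, the gain is at most about 1 point of power.

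**The Day 8 analysis might be read as unable to show any effect of serostatus.** The documents do not support that. SAP 7 does not name serology, SAP 6.3.3 lists it as a baseline characteristic, and symptom duration is not a biomarker at all. The text under SAP 6.4.4 (Subgroup Analyses) is not visible, so a serostatus subgroup may already be planned. What remains is an ambiguity that the SAP should settle.

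**Dilution might be read as a demonstrated flaw.** If -1.5 applied to seronegative patients only and seropositive patients gained nothing, the pooled effect would be -1.5(1-s). That is -1.20 at 20% and -0.75 at 50%, and it falls short of -1 once s exceeds one third. SAP 5 does not say that -1.5 is a seronegative effect. If it describes the mixed population, there is no further loss. Main-effect covariates would not remove dilution in any case.

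**Conclusion.** The point holds as one of efficiency and clarity. Two predictors that the protocol's own rationale points to are measured before dosing and summarized at baseline, but are not used in the primary model. Using them would gain roughly 0.2 to 3.5 points of power without more patients, and would adjust for chance differences of the order of 0.16-0.21 log10 in a dose contrast at the upper assumed shifts. The range is wide because the seropositive share and the residual shift are assumptions; at smaller shifts the benefit is close to nil. The dilution figures remain a what-if and do not support this change. The change is worth making because it is nearly free before the lock and post hoc afterwards.

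**What to change.** In SAP 6.4.1, add baseline serostatus (positive, negative, missing) and days from first symptom to dosing as prespecified fixed effects, each with a visit interaction. Align Protocol 10.2.1, or record the difference in SAP 8.

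In SAP 7, state that Day 1 serology is a baseline covariate, will be assayed before the primary lock, and is not among the excluded exploratory biomarkers.

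If SAP 6.4.4 does not already provide for it, a Day 8 treatment-by-serostatus estimate may be reported as supportive only. At 20-50% seropositive it would rest on about 41 × 0.8 = 33 down to 41 × 0.5 = 20 seronegative patients per arm, with mean power of about 65% down to 48% even for the full planned effect. SAP 6.2.4 provides no multiplicity adjustment beyond MCPMod, so this estimate should not become a second route to dose selection.

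The cost is SAP wording, about 2 degrees of freedom per visit (3 if the missing-serology level is used), and earlier assay of samples the protocol already collects.
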